6.3 Subject Exclusion Criteria

1. Involvement in the planning and/or conduct of the study (applies to both AstraZeneca staff and/or staff at the study site); Previous enrollment in the present study.
2. Participation in another clinical study with receipt of an investigational product during the last 4 weeks.
3. Any previous treatment with a PD-1 or PD-L1 inhibitor, including durvalumab or any anti-CTLA4, including tremelimumab.
4. History of another primary malignancy except for:

Date:

- Malignancy treated with curative intent and with no known active disease ≥ 3 years before the first dose of study drug and of low potential risk for recurrence
 - Adequately treated non-melanoma skin cancer or lentigo maligna without evidence of disease
 - Adequately treated carcinoma in situ without evidence of disease (eg, cervical cancer in situ)
 - Adequately treated stage 1 breast cancer.
5. Receipt of the last dose of anti-cancer therapy (chemotherapy, immunotherapy, targeted therapy, biologic therapy, tumor embolization, monoclonal antibodies) < 21 days prior to the first dose of study drug. Receipt of the last dose of hormonal therapy within < 7 days prior to the first dose of study drug.
 6. Any prior radiation therapy must be discontinued at least four weeks prior to registration.
 7. At least 4 weeks must have elapsed since the patient underwent any major surgery (e.g., major: laparotomy, laparoscopy) There is no delay in treatment for minor procedures (e.g., central venous access catheter placement).
 8. Patients should not be candidates for further surgical resection or definitive tumor-directed XRT based upon prior therapies and/or extent of disease at recurrence.
 9. Mean QT interval corrected for heart rate (QTc) ≥ 470 ms calculated from 3 electrocardiograms (ECGs)
 10. Current or prior use of immunosuppressive medication within 28 days before the first dose of durvalumab or durvalumab and tremelimumab, with the exceptions of intranasal and inhaled corticosteroids or systemic corticosteroids at physiological doses, which are not to exceed 10 mg/day of prednisone, or an equivalent corticosteroid. Patients who have received acute, low dose, systemic immunosuppressant medications (e.g., dexamethasone for nausea or steroids as CT scan contrast premedication) may be enrolled.
 11. Any prior Grade ≥ 3 immune-related adverse event (irAE) while receiving any previous immunotherapy agent, or any unresolved irAE > Grade 1

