11.1 TOXICITIES/SIDE EFFECTS

The dose delay and reduction instructions provided in this section are intended to serve as guidelines to allow ongoing treatment for patients experiencing clinical benefit without signs or symptoms of progression while ensuring patient safety. Patients may temporarily suspend dosing of study drug for up to 14 days if they experience toxicity that is considered related to study drug and requires that a dose be held. Patients who miss ≥ 28 consecutive days of scheduled study treatment because of drug-related AEs will be discontinued from the study. Exceptions may be made after discussion with and approval by the Principal Investigator.

Patients may suspend dosing of study drug for radiation therapy or surgery that is considered by the treating physicians to be of clinical benefit for the patient. After completion of the intervention, patients may restart the study drug as long as all criteria for dosing are met and there is no evidence of disease progression (unless approved by PI and sponsor as noted previously).

For adverse events (AEs) that are considered at least partly due to administration of durvalumab or tremelimumab the following dose adjustment guidance may be applied:

Date:

- Treat each of the toxicities with maximum supportive care (including holding the agent suspected of causing the toxicity where required).
- If the symptoms promptly resolve with supportive care, consideration should be given to continuing the same dose of durvalumab or tremelimumab along with appropriate continuing supportive care.
- In addition, there are certain circumstances in which durvalumab or tremelimumab should be permanently discontinued.

Following the first dose of durvalumab or tremelimumab, subsequent administration of durvalumab or tremelimumab can be modified based on toxicities observed (see Table 4). Dose reductions are not permitted

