Restricted, prohibited, and permitted concomitant medications are described in the following tables. Refer to Section 6.6 for guidance on management of IP-related toxicities.

Date:

Investigators may prescribe concomitant medications or treatments (e.g., acetaminophen, diphenhydramine) deemed necessary to provide adequate prophylactic or supportive care except for those medications identified as “excluded” as listed below.

Excluded Concomitant Medications

The following medications are considered exclusionary during the study.

1. Any investigational anticancer therapy other than the protocol specified therapies
2. Any concurrent chemotherapy, radiotherapy (except palliative radiotherapy), immunotherapy, biologic or hormonal therapy for cancer treatment, other than the protocol specified therapies. Concurrent use of hormones for noncancer-related conditions (e.g., insulin for diabetes and hormone replacement therapy) is acceptable. NOTE: Local treatment of isolated lesions for palliative intent is acceptable (e.g., by local surgery or radiotherapy)
3. Immunosuppressive medications including, but not limited to systemic corticosteroids at doses not exceeding 10 mg/day of prednisone or equivalent, methotrexate, azathioprine, and TNF- α blockers. Use of immunosuppressive medications for the management of investigational product-related AEs or in subjects with contrast allergies is acceptable. In addition, use of inhaled and intranasal corticosteroids is permitted. A temporary period of steroids will be allowed for different indications, at the discretion of the principal investigator (e.g., chronic obstructive pulmonary disease, radiation, nausea, etc).
4. Live attenuated vaccines within 30 days of durvalumab dosing (ie, 30 days prior to the first dose, during treatment with durvalumab and for 30 days post discontinuation of durvalumab. Inactivated vaccines, such as the injectable influenza vaccine, are permitted.

Date:

Table 8. Prohibited and Rescue Medications

Prohibited medication/class of drug:	Usage:
Additional investigational anticancer therapy concurrent with those under investigation in this study	Should not be given whilst the patient is on IP treatment
mAbs against CTLA-4, PD-1, or PD-L1	Should not be given whilst the patient is on IP treatment through 90 days after the last dose of IP.

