Any concurrent chemotherapy, local therapy (except palliative radiotherapy for non-target lesions, eg, radiotherapy, surgery, radiofrequency ablation), biologic therapy, or hormonal therapy for cancer treatment	Should not be given whilst the patient is on IP treatment (including SoC). (Concurrent use of hormones for non-cancer-related conditions [eg, insulin for diabetes and hormone replacement therapy] is acceptable.)
Immunosuppressive medications, including, but not limited to, systemic corticosteroids at doses exceeding 10 mg/day of prednisone or its equivalent, methotrexate, azathioprine, and tumor necrosis factor α blockers	Should not be given whilst the patient is on IP treatment (including SoC). (Use of immunosuppressive medications for the management of IP-related AEs or in patients with contrast allergies is acceptable. In addition, use of inhaled, topical, and intranasal corticosteroids is permitted.
Live attenuated vaccines	Should not be given through 30 days after the last dose of IP (including SoC) during the study

Rescue/supportive medication/class of drug:	Usage:
Concomitant medications or treatments (eg, acetaminophen or diphenhydramine) deemed necessary by the Investigator to provide adequate prophylactic or supportive care, except for those medications identified as “prohibited” as listed above	To be administered as prescribed by the Investigator
Best supportive care (including antibiotics, nutritional support, growth factor support, correction of metabolic disorders, optimal symptom control, and pain management [including palliative radiotherapy, etc])	Should be used when necessary for all patients
Best supportive care (including antibiotics, nutritional support, growth factor support, correction of metabolic disorders, optimal symptom control, and pain management [including palliative radiotherapy, etc])	Should be used when necessary for all patients

Blood donation

Subjects should not donate blood while participating in this study, or for at least 90 days following the last infusion of durvalumab or tremelimumab.

Date:

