12.2 Disease Parameters

Date:

Measurable disease. Measurable lesions are defined as those that can be accurately measured in at least one dimension (longest diameter to be recorded) as >20 mm by chest x-ray, as >10 mm with CT scan, or >10 mm with calipers by clinical exam. All tumor measurements must be recorded in millimeters (or decimal fractions of centimeters).

Note: Tumor lesions that are situated in a previously irradiated area will not be considered measurable unless progression is documented or a biopsy is obtained to confirm persistence at least 90 days following completion of radiation therapy.

Malignant lymph nodes. To be considered pathologically enlarged and measurable, a lymph node must be ≥ 15 mm in short axis when assessed by CT scan (CT scan slice thickness recommended to be no greater than 5 mm). At baseline and in follow-up, only the short axis will be measured and followed.

Non-measurable disease. All other lesions (or sites of disease), including small lesions (longest diameter <10 mm or pathological lymph nodes with ≥ 10 to <15 mm short axis), are considered non-measurable disease. Bone lesions, leptomeningeal disease, ascites, pleural/pericardial effusions, lymphangitis cutis/pulmonitis, inflammatory breast disease, and abdominal masses (not followed by CT or MRI), are considered as non-measurable.

Note: Cystic lesions that meet the criteria for radiographically defined simple cysts should not be considered as malignant lesions (neither measurable nor non-measurable) since they are, by definition, simple cysts.

'Cystic lesions' thought to represent cystic metastases can be considered as measurable lesions, if they meet the definition of measurability described above. However, if non-cystic lesions are present in the same patient, these are preferred for selection as target lesions.

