12.4 Response Criteria

Evaluation of Target Lesions

Complete Response (CR): Disappearance of all target lesions. Any pathological lymph nodes (whether target or non-target) must have reduction in short axis to < 10 mm.

Partial Response (PR): At least a 30% decrease in the sum of the diameters of target lesions, taking as reference the baseline sum diameters.

Progressive Disease (PD): At least a 20% increase in the sum of the diameters of target lesions, taking as reference the smallest sum on study (this includes the baseline sum if that is the smallest on study). In addition to the relative increase of 20%, the sum must also demonstrate an absolute increase of at least 5 mm. (Note: the appearance of one or more new lesions is also considered progressions).

Stable Disease (SD): Neither sufficient shrinkage to qualify for PR nor sufficient increase to qualify for PD, taking as reference the smallest sum diameters while on study.

Evaluation of Non-Target Lesions

Complete Response (CR): Disappearance of all non-target lesions and normalization of tumor marker level. All lymph nodes must be non-pathological in size (< 10 mm short axis). Note: If CA125 is initially above the upper normal limit, it must normalize for a patient to be considered in complete clinical response.

Non-CR/Non-PD: Persistence of one or more non-target lesion(s) and/or maintenance of CA125 level above the normal limits.

Date:

Progressive Disease (PD): Appearance of one or more new lesions and/or unequivocal progression of existing non-target lesions. Unequivocal progression should not normally trump target lesion status. It must be representative of overall disease status change, not a single lesion increase.

Although a clear progression of “non-target” lesions only is exceptional, the opinion of the treating physician should prevail in such circumstances, and the progression status should be confirmed at a later time by the review panel (or Principal Investigator).

Evaluation of Best Overall Response

The best overall response is the best response recorded from the start of the treatment until disease progression/recurrence (taking as reference for progressive disease the smallest measurements recorded since the treatment started). The patient's best response assignment will depend on the achievement of both measurement and confirmation criteria.

For Patients with Measurable Disease (i.e., Target Disease)

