16.2 Quality Assurance

The Principal Investigator is responsible for ensuring that all staff involved in the study is familiar with the content of this section.

The data and safety monitoring plan at Memorial Sloan Kettering Cancer Center was approved by the National Cancer Institute in September 2001. The plan addressed the new policies set forth by the NCI and the document entitled "Policy of the National Cancer Institute for data and safety monitoring of clinical trials" which can be found at <http://grants.nih.gov/grants/guide/noticefiles/not98-084.html>. The DSM plans at MSKCC were established and are monitored by the Office of Clinical Research. The MSKCC data and safety monitoring plan can be found on the MSKCC Internet at

[http://inside2.clinresearch/Documents/MSKCC Data and Safety Monitoring Plans.pdf](http://inside2.clinresearch/Documents/MSKCC%20Data%20and%20Safety%20Monitoring%20Plans.pdf). There are several different mechanisms by which clinical trials are monitored for data, safety and quality. There are institutional processes in place for quality assurance (e.g., protocol monitoring, compliance and data verification audits, therapeutic response, and staff education on clinical research QA) and departmental procedures for quality control, plus there are two institutional committees that are responsible for monitoring the activities of our clinical trials programs. Memorial Sloan Kettering Cancer Center has set up three distinct monitoring processes for our clinical trials program. There are two sub-committees that have the responsibility of data and safety monitoring. These are joint sub-committees with dual-reporting responsibilities. The Data and Safety Monitoring Committee (DSMC) is the sub-committee responsible for monitoring all Phase 1, 2, 1/2, pilot and non-phase clinical trials. The Data and Safety Monitoring Board (DSMB) is the sub-committee responsible for monitoring Phase 3 randomized clinical trials. The Therapeutic Response Review Committee (TRRC) is the sub-committee of Research Council responsible for the independent therapeutic response review for participants in IRB/PB approved clinical trials where therapeutic efficacy is a stated primary objective, typically phase 2 and 3 trials. Formal monitoring of such studies is designed to ensure that the interests of the participants are being scrutinized on a regular basis, and that the trial is progressing in a satisfactory manner.

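### Excluded-medication item 2 accepts palliative local surgery or radiotherapy to any isolated lesion, against Table 8's non-target limit, and Sections 12 and 14 do not say how a locally treated target lesion is scored in the primary ORR

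*Combined protocol and SAP*

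**What the plan says.** **Permissions and limits on local therapy (Section 11)**

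- Excluded Concomitant Medications, item 2, exempts palliative radiotherapy from the exclusion and adds a note: "Local treatment of isolated lesions for palliative intent is acceptable". The note gives local surgery and radiotherapy as examples. Neither part mentions target lesions.
- Table 8, prohibited row, lists among treatments not to be given on study treatment "local therapy (except palliative radiotherapy for non-target lesions, eg, radiotherapy, surgery, radiofrequency ablation". Surgery and ablation are therefore barred, and palliative radiotherapy is allowed only to non-target lesions.
- Table 8, supportive-care row, allows "pain management [including palliative radiotherapy, etc" for all patients when needed, without repeating the non-target limit.
- Section 11.1 states: "Patients may suspend dosing of study drug for radiation therapy or surgery", where the treating physicians judge it beneficial. Dosing may restart if dosing criteria are met and there is no progression, unless an exception is approved.

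**Scoring (Sections 12 and 14)**

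- PR is "At least a 30% decrease in the sum of the diameters of target lesions" relative to baseline (Section 12.4). Best overall response runs from treatment start to progression or recurrence.
- Endpoints are derived programmatically from RECIST v1.1 (Section 12.4, Permitted Deviations from RECIST).
- The nearest text on treated lesions is in Section 12.2: "Tumor lesions that are situated in a previously irradiated area will not be considered measurable unless progression is documented", or a biopsy confirms persistence.
- Section 14.0 analyses response-evaluable patients, with no provision for local therapy given on study. An arm continues with at least 3 responders in 27 and is declared positive with at least 7 in 40.

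**The concern.** An investigator who follows item 2 can breach Table 8. Palliative resection of an isolated lesion is acceptable under the first and barred under the second. Palliative radiotherapy to a target lesion is likewise within item 2 and outside Table 8.

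The conflict touches the primary endpoint because PR depends on the sum of target diameters. If a target lesion is removed or irradiated before progression, the sum falls for a reason unrelated to study drug. The response window does not close at local therapy, and the written scoring rules do not set the treated lesion aside. The footnote to the best-response table ties its confirmation requirement to non-randomized trials, so in this randomized study a single scan after the procedure may be enough. With thresholds of 3/27 and 7/40, one responder can decide an arm.

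**Working it through.** **1. The texts side by side**

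| Text | Surgery | Palliative radiotherapy | Applies |
|---|---|---|---|
| Item 2 | accepted for isolated lesions | accepted, any lesion | during the study |
| Table 8, prohibited row | barred | non-target lesions only | on study treatment |
| Table 8, supportive-care row | not mentioned | accepted, no limit stated | when necessary |
| Section 11.1 | permitted | permitted (radiation in general) | while dosing is suspended |

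Item 2 and the prohibited row give opposite answers on surgery and different answers on palliative radiotherapy to a target lesion. The other two rows of the table are softer points (see the objection).

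**2. When could local therapy alone produce a PR?**

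Suppose a treated lesion makes up a share s of the baseline sum, disappears, and the other target lesions do not change. The sum then falls by s, so PR needs s ≥ 30%. With equal-sized lesions, s is 1/5 = 20% for five targets, 1/4 = 25% for four and 1/3 = 33% for three. One removed lesion is then enough only with three or fewer targets. Unequal sizes change this, and partial shrinkage after radiotherapy needs a larger share.

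**3. The plan's own design figure**

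Inputs from Section 14.0: p0 = 0.10, p1 = 0.25, at least 3/27 to continue, at least 7/40 to declare positive, 10% type I error, 90% power.

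P(positive | p) = Σ over x = 3…27 of P[Bin(27, p) = x] × P[Bin(13, p) ≥ 7 − x]

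- p = 0.10: 0.0977
- p = 0.25: 0.9001

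The stated design reproduces.

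**4. One artefactual responder in an arm with a true ORR of 10%**

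- In stage 1: Σ over x = 2…26 of P[Bin(26, 0.10) = x] × P[Bin(13, 0.10) ≥ 6 − x] = 0.189
- In stage 2: Σ over x = 3…27 of P[Bin(27, 0.10) = x] × P[Bin(12, 0.10) ≥ 6 − x] = 0.183
- Stage 1 rule alone: P[Bin(27, 0.10) ≥ 3] = 0.515 becomes P[Bin(26, 0.10) ≥ 2] = 0.749

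**5. An assumed mis-scoring rate**

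The documents give no rate of on-study local therapy. Let q be an assumed share of true non-responders scored CR or PR for this reason. The effective response rate is 0.10 + 0.90q. With 40 × 0.90 = 36 expected non-responders per arm:

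| q (assumed) | Expected patients per arm (36q) | Effective rate | False-positive chance |
|---|---|---|---|
| 0 | 0 | 0.1000 | 9.8% |
| 0.25% | 0.09 | 0.10225 | 10.7% |
| 0.5% | 0.18 | 0.1045 | 11.7% |
| 1% | 0.36 | 0.109 | 13.7% |
| 2% | 0.72 | 0.118 | 18.4% |

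**6. Power cost of a rule that discounts later responses**

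If an assumed 1% of true responders were lost, the rate at the target is 0.25 × 0.99 = 0.2475 and power is 0.894. At 2%, it is 0.25 × 0.98 = 0.245 and power is 0.887. The starting value is 0.900.

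**The case against.** **Only item 2 clearly conflicts with Table 8.** A reader might infer that Section 11.1 and the supportive-care row contradict it too. The documents do not support that. Section 11.1 covers radiation or surgery while dosing is suspended, whereas the prohibited row applies while the patient is on study treatment, so the two can be read together. The supportive-care row sits in the same table and can be read as limited by the more specific row. The text before the tables also refers the reader to them for permitted and prohibited treatments, which favours Table 8 as the operative text. This objection stands, and it narrows the point to item 2.

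**A rule may exist outside the protocol.** A reader might infer that nothing at all prevents such a case from being scored as a response. That goes too far. Response follows the cited RECIST 1.1 guideline, which is not among the documents. What can be shown is that Sections 12 and 14 as written state no rule.

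**The route is narrow, and there are safeguards.** The patient must not have progressed, and the treated lesion must carry enough of a sum of up to five lesions. At entry, "Patients should not be candidates for further surgical resection or definitive tumor-directed XRT". A committee is "responsible for the independent therapeutic response review for participants" in trials of this kind. All of this makes the event uncommon, but none of it settles the scoring. The exclusion applies at entry and does not address palliative treatment. The committee is given no rule for treated lesions. The irradiated-area note defines measurability and does not cover surgery or ablation. Section 13 makes alternative anticancer therapy a reason to stop drug and gives no scoring rule.

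**The calculations are not evidence of frequency.** Any single mis-scored responder would have the same effect on the two-stage rule. That is correct, and the figures should not raise the weight of the point.

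**Conclusion.** The point holds as a minor one. Item 2 and Table 8's prohibited row disagree on local therapy during study treatment, and the written scoring rules would let shrinkage caused by that therapy count towards the primary ORR.

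The size is conditional. One such patient in an arm with a true ORR of 10% would roughly double its false-positive chance, from 9.8% to 18-19%. If the case fell in stage 1, the chance of continuing would rise from 51.5% to 74.9%. Under assumed mis-scoring rates of 0.25% to 2%, the false-positive chance runs from 10.7% to 18.4%.

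A reader might take these figures to mean that the trial's type I error is understated. The documents do not support that: the design reproduces its stated error rates, and no rate of on-study local therapy is given. Confidence is medium, because the cited response guideline could not be consulted and the event should be uncommon.

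**What to change.** **1. Section 11 wording.** Align item 2 with Table 8's existing limit: while a patient is receiving study drug, the only local therapy allowed is palliative radiotherapy to non-target lesions. Cross-refer the supportive-care row to that limit. Leave Section 11.1's permission for beneficial radiation or surgery during a suspension as it is. Removing it would be a patient-care trade-off that this concern does not justify.

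**2. A scoring rule in Section 14.0.** Suggested text: *A CR or PR first documented after local therapy to a target lesion does not count as a response in the primary ORR analysis, including the stage 1 and final decision rules. The patient remains in the denominator as a non-responder. A response documented before the local therapy still counts.* This is still needed once item 2 is aligned, because local therapy can be given during a suspension, after drug has stopped without progression, or as a deviation. Scoring such patients as not evaluable would be an alternative. Keeping them in the denominator is the more conservative choice.

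**3. Data.** Record the date, the lesion treated and its target status for every on-study local therapy. Appendix A lists palliative radiotherapy only in post-treatment follow-up, without lesion or target status.

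**Cost.** This is a wording change, one short scoring rule and a few data fields; the sample size and decision thresholds do not change. An occasional genuine later response would not be counted. If an assumed 1% or 2% of true responders were lost this way, power at a 25% ORR would fall from 90.0% to 89.4% or 88.7%.
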